- 2) Achieving higher local concentrations of medication with tourniquet inflation leading to a "pooling effect", therefore maximising local analgesia and resulting in overall more efficacious pain relief.
- 3) Potentially prolonged duration of action of the medication given IO access may produce a depot effect.
- 4) The ability to provide rapid regional administration of medication through an intraosseous cannulation, avoiding the need to cannulate a foot vein.
- 5) Indirect benefit of lowering postoperative systemic opiate consumption due to more effective pain relief, therefore avoiding or reducing the undesired side effects that come with opioids.
- 6) With enhanced early postoperative pain control this may allow for a faster recovery through early mobilisation

Patient Evaluation Schedule

Evaluation	History/Pre -op	Post-op first 24 hours (1-5 hrs, 12 hrs, 24 hrs)	Post-op day 1	Discharge date	1 week post-op	Week 2	Week 6
Demographics	х						
Medical History	х						
Allocated Analgesia	х						
PCS	х						
PDI	х						
KOOS Jr Score	х					х	х
окѕ	х					х	х
VAS-P	х	х			х		
ММЕ	х	х			х		
LoS				х			
Gait					х		
Sleep					х		
QoR-15			х				
Satisfaction						х	х

Visit Windows

Definition – Since it is not always possible for subjects to come in for a study visit on the exact date, most protocols allow a certain time period before or after the calendar date; this is known as the visit window. If a subject is not seen during the visit window, that visit will be regarded as a missed visit. Visit windows are calculated in reference to the baseline date, which is the surgery date (intra-op) for this study.

Visit windows:

• Pre-op: within 6 months before date of surgery

• Week 2: +/- 1 week

• Week 6: +/- 2 weeks

Objectives

The primary objective of this study is:

 To demonstrate that preoperative IORA Diclofenac (Voltaren™) is superior to systemic (intravenous) Diclofenac, in providing early pain control following primary total knee arthroplasty (TKA) for osteoarthritis. Visual analogue scale pain (VAS-P) scores will be the primary outcome to compare pain at rest and with standard evoked movement; means will be calculated over 1 week.

The secondary objectives of this study are:

- Comparing MME measurements between the IORA Diclofenac, and systemic Diclofenac groups to demonstrate reduced postoperative systemic opioid use for additional pain relief with IORA technique.

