The minimal clinically important difference is defined as the smallest change in a measurement that signifies an important improvement in a symptom. MCID for VAS-P in acute pain management has a wide range, ranging from 8-40 mm, with a median of 17 mm [29]. In a review across 570 randomised controlled trials on postoperative pain management after total hip and knee arthroplasty, the median MCID for VAS-P was found to be 15 mm at rest and 18 mm during movement [30]. Another study demonstrated the mean MCID for VAS postoperative pain improvement in TKA patients to be 22.6 mm [33]. There is yet to be a standardised value for postoperative VAS-P MCID, but based on recent literature and consensus we have chosen an MCID of 20 mm to suggest clinically relevant improvements in pain relief between the intervention and control groups [34].

Using this data, a priori power analysis was calculated using this data, which found that 22 patients in each arm would provide >95% statistical power to detect the expected difference in pain relief (MCID of 20 mm) at the 5% significance level between IORA Diclofenac and systemic (IV) Diclofenac. An additional patient in each group (5%) will bring each group to 23 patients to account for loss of follow up.

Inclusion Criteria

Informed consent obtained - both written and verbal

Patient undergoing primary total knee arthroplasty for Osteoarthritis

Age \geq 18 and \leq 80 years old (inclusive)

Exclusion Criteria

Patient lacking capacity to consent to the research project

BMI ≥ 40

Pregnancy or suspected pregnancy

Pain Catastrophising Scale score ≥ 30 points

Previous infection of knee joint

Rheumatoid/inflammatory arthritis

Undergoing bilateral total knee replacement, revision total knee arthroplasty, or any additional procedure outside of a primary total knee arthroplasty

Precluded from having general anaesthesia

Patients with lower limbs not amenable to effective tourniquet use

Contraindications to Diclofenac:

[figure not shown]
- Established allergy or hypersensitivity to Aspirin or other NSAID including attacks of asthma, angioedema, urticaria, or acute rhinitis
- Severe renal disease (GFR<30 mL/min/1.73m²)
- Severe cardiac failure
- Hepatic failure
- Active gastric or intestinal ulcer, bleeding or perforation
- Recent myocardial infarction (within last 12 months)
- History of asthma
- History of haemorrhagic diathesis

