A patient reported outcome questionnaire to measure the quality of recovery after anaesthesia, which is important in determining early postoperative health status of patients.

Outcomes

Preoperative Outcome Measurements

The following outcome measurements will need to be completed by patients prior to their surgery. Baseline scores will be averaged for each study group:

- PCS A PCS score of ≥ 30 represents clinically relevant catastrophising and will exclude patients from the study.
- PDI
- KOOS, Jr
- OKS
- Preoperative VAS-P score
- Preoperative opioid use (MME) Participants will be required to report any and all opioid
 pain medications (including Tramadol and Codeine) they use as well as the average daily
 amount of opioid medications in milligrams that they take. For example, 20 mg of Sevredol
 daily. This will be converted into a preoperative baseline MME.

Postoperative Outcome Measurements

The primary outcome of this study will be patient pain levels during the early stages of recovery following primary total knee arthroplasty. To monitor this, pain at rest scores will be recorded by the patient using the Visual Analogue Scale (VAS; 0-100 mm from "no pain" to "worst pain possible"). The distance between "no pain" and the patient-made mark is to be measured to the nearest 1 mm.

Post-operatively, once the patient has arrived at the recovery unit, pain scores are to be recorded at the following time points: 1 hour, 2 hours, 3 hours, 4 hours, 5 hours, 12 hours, and 24 hours post-op. These numbers will be recorded by a recovery nurse who will be blinded to the treatment group, and by a treating physio the following day. Patients will also record twice daily VAS-P scores at 8am and 5pm from post-op day 1, up to post-op day 7, into a pain diary supplied to them. These twice daily recordings will be used to calculate daily averages of pain scores. All VAS-P scores are to be recorded for 'pain at rest'.

The minimal clinically important difference (MCID) of 20 mm for VAS-P scores will be used to determine the clinical significance of pain relief in the intervention group compared to the control group.

Secondary outcomes which focus on function, pain, satisfaction, and health related quality of life:

• Total Morphine Milligram Equivalent (MME) of additional postoperative opioid medications required for 1 week post-op (from post-op day 0 to post-op day 7).

- Quality of recovery after anaesthesia (as per QoR-15 survey), recorded post-op day 1.

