Means, standard deviation, and 95% confidence intervals will be calculated for the participant VAS-P scores at each recorded time interval as the primary objective of the study. A general linear model or generalised linear mixed model, followed by independent two-sample t-test or Wilcoxon non-parametric rank sum test will be used to analyse the data. VAS-P scores will be pooled according to the appropriate study group for comparison between the study arms. An MCID of 20 mm will be used to determine a clinically significant difference in pain management (but not necessarily statistical significance).

For secondary objectives, independent two-sample t-test or Wilcoxon non-parametric rank sum test will be used to compare means of MME, LoS, QoR-15, satisfaction, gait, sleep, OKS, KOOS Jr scores between the intervention group and control group.

The intended statistical test used will be dependent on the distribution of the data collected. This will be determined by appropriate normality and homogeneity testing of the data. If requirements

are not met, a transformation may be applied, which will likely be logarithmic. Adjustments will be made accordingly based on the data obtained.

Baseline characteristics and preoperative survey scores will be compared using a two sample t-test or Wilcoxon non-parametric rank sum test. Gender comparisons between the two study groups will need to be analysed using a two-way analysis of variance (ANOVA) or in the case of non-parametric testing, Kruskal-Wallis test.

Adverse events will be recorded separately and reviewed by investigators for relevance to the procedure/intervention as well as commonalities. Frequency and percent distributions will be presented in tabular form and logistic regression will be used for comparison of the study groups.

The statistical principles of this protocol have been reviewed by a Consultant Statistician who will also oversee statistical analysis.

Selection Criteria for Investigators/Sites

- The investigator(s) participating in this study is(are) qualified Orthopaedic surgeon(s).
- Research assistants and study staff will be under the direction of the Principal investigator.
- Conflicts of interest (including financial assistance from other parties) will be declared by Investigators and research personnel before starting the trial.
- A list entailing any persons, their qualifications, and their roles relating to the trial, must be kept by the investigators.

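### The primary outcome is worded in three ways, and no single contrast is named to decide the superiority claim

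*Protocol*

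**What the plan says.** Four places in the protocol bear on the primary outcome.

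- **Objectives.** The aim is to show superiority in early pain control. VAS-P is to "compare pain at rest and with standard evoked movement; means will be calculated over 1 week".
- **Postoperative Outcome Measurements.** "The primary outcome of this study will be patient pain levels during the early stages of recovery", with no time point or summary measure named. Hospital readings are taken at "1 hour, 2 hours, 3 hours, 4 hours, 5 hours, 12 hours, and 24 hours post-op". Patients also record "twice daily VAS-P scores at 8am and 5pm from post-op day 1, up to post-op day 7" in a diary, and "These twice daily recordings will be used to calculate daily averages of pain scores". The paragraph ends by saying that all VAS-P scores are for pain at rest.
- **Data Capture and Analysis.** Means, SDs and 95% confidence intervals are to be "calculated for the participant VAS-P scores at each recorded time interval as the primary objective of the study". A general linear or generalised linear mixed model comes next, followed by a two-sample t-test or a rank-sum test. Scores are then said to be pooled by study group for the comparison of arms.
- **Power Calculation.** The calculation gives 22 patients per arm and more than 95% power for a 20 mm difference "at the 5% significance level between IORA Diclofenac and systemic (IV) Diclofenac".

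**The concern.** A superiority trial needs one stated quantity whose result decides the claim. Here the three descriptions differ in the period covered (a week, the early stages of recovery, each interval), in the condition measured (rest and movement, or rest only) and in whether the result is a summary or a series. The follow-on tests have no stated unit, so a reader cannot tell whether they apply to one value per patient or to each interval.

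The consequence is that the deciding comparison could be chosen after the data are seen. The 5% level and the power were set for a single comparison, and nothing in the text says which comparison that is.

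**Working it through.** **1. The definitions side by side**

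| Section | Condition | Time frame | Form |
|---|---|---|---|
| Objectives | rest and evoked movement | 1 week | means, level of averaging not stated |
| Postoperative Outcome Measurements | rest only | early stages of recovery | none named |
| Data Capture and Analysis | not stated | each recorded interval | a series of means |
| Power Calculation | not stated | planning data at 48 h and 72 h | one 20 mm difference |

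**2. Number of intervals.** There are 7 hospital readings. The diary gives 2 × 7 = 14 readings, reduced to 7 daily averages. The total is 7 + 7 = 14 intervals.

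**3. The plan's own figure.** Inputs from Power Calculation: difference 20 mm, 22 per arm, 5% level (two-sided assumed), and the SDs of the cited celecoxib trial.

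- Pooled SD at 48 h: √((16.8² + 15.0²)/2) = 15.9. At 72 h: √((16.6² + 20.1²)/2) = 18.4.
- Standardised difference 20/(SD × √(2/22)): 4.17 at 48 h, 3.60 at 72 h.
- Power by the normal approximation, Φ(standardised difference − 1.96): 98.6% and 94.9%. By the noncentral t: about 98% and 94%.

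The stated 22 per arm with more than 95% power therefore reproduces, closely enough, for one comparison at one interval.

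**4. Error rate if all 14 intervals were tested unadjusted.** This is a conditional calculation, because the protocol does not state such testing. If the intervals were independent, the chance of at least one false positive would be 1 − 0.95^14 = 51.2%. Repeated scores in one patient are correlated, so that is an upper illustration. The table comes from simulation under no effect: normal scores, 22 per arm, a two-sided 5% t-test at each interval and equal correlation between intervals. The correlations are assumptions, since the protocol gives none.

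| Correlation | Any false positive | False positive favouring the intervention |
|---|---|---|
| 0.3 | 44% | 23% |
| 0.5 | 36% | 18% |
| 0.7 | 25% | 13% |
| 0.9 | 14% | 7% |

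Simulation error is about one percentage point. If correlation instead decays with distance in time (first-order autoregressive), the any-direction rates are 46%, 39% and 24% at adjacent correlations of 0.5, 0.7 and 0.9.

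**5. Error rate with one value per patient.** Averaging each patient's 14 values and testing the averages once gave about 5% at every correlation tried.

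**The case against.** The strongest reply is that the analysis section can be read benignly. The sentence about each interval promises description only. The test sentence puts a model first, so the follow-on tests may depend on its result, and the pooling sentence may mean one overall comparison. In the simulation, a single comparison, or interval tests made only after a significant test of the weekly mean, kept the rate at 5% or below. The plural in the Objectives can also be read as means at each interval across the week, which would agree with the analysis section. Finally, a multiplicity rule is often left to the statistical analysis plan, which is not at hand.

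Much of this stands, and it rules out three stronger readings that a reader might infer:

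- That each time point is tested at 5%. The protocol does not say so, and the rates in the table are conditional on it.
- That the Objectives plainly define one mean per patient. They are ambiguous.
- That the stated power fits none of the definitions. It reproduces for a single interval, and the 48 h and 72 h values are planning inputs, not another outcome definition.

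The absence of a multiplicity rule is likewise not the point here.

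What the reply does not remove is the inconsistency itself. The benign reading is not written either: no dependence on the model result is stated, and pooling by group protects the error rate only if each patient contributes one value. Rest and movement in one section against rest only in another is a direct conflict on any reading.

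**Conclusion.** The concern holds as an unfixed and inconsistently worded primary outcome. No single contrast decides superiority, and the one comparison that was powered at 5% is not tied to any of the three descriptions. The effect on the error rate depends on how the gap is filled. It is about 5% if one value per patient is tested once, and about 14% to 44% if 14 intervals are tested unadjusted with equal correlations of 0.9 down to 0.3, roughly half of that favouring the intervention. Those figures assume normal scores, 22 per arm and two-sided tests. Fixing the primary contrast belongs in the protocol, and it should be done before any unblinded data are examined.

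**What to change.** Use the same wording in Objectives, Postoperative Outcome Measurements, and Data Capture and Analysis:

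1. Name one primary contrast. One example is the between-arm difference in VAS-P at rest averaged over the first post-operative week, estimated as a single treatment contrast from one linear mixed model with patient as random effect, at two-sided 5%.
2. State in advance how the readings are averaged. All 7 hospital readings fall in the first 24 hours, so the choice affects what the average represents.
3. Reconcile the evoked-movement wording in the Objectives with the rest-only recording.
4. Report individual time points with estimates and confidence intervals as secondary, without superiority claims.
5. Tie the sample size statement to the chosen contrast. The stated power carries over only if 20 mm and the planning SDs are reasonable for it.

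The cost is wording and the ethics approval that the protocol requires for any modification; no new data are needed. The downside is that an isolated difference at one time point can no longer support superiority. Keeping all 14 intervals primary under Bonferroni would cost more: 0.05/14 = 0.0036 per test, with power per comparison at 22 per arm of 85% (SD 15.9) or 69% (SD 18.4).

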- Quality of life/functional outcome comparisons using the KOOS Jr score, Oxford Knee Score (OKS), numerical rating scales (NRS) of gait/walking ability and sleep.
- Post-operative recovery comparisons using the Quality of Recovery 15 (QoR-15) survey and comparing average length of stay (LoS) for each study group

Questions to be answered:

- Is IORA of Diclofenac or systemic Diclofenac more effective in managing post-operative pain (as judged by VAS-P scores).
- 2. Will IORA of combined Diclofenac or systemic Diclofenac result in a more significant reduction in additional systemic opioid use for post-operative analgesia (as judged by MME).
- 3. Will IORA of Diclofenac or systemic Diclofenac provide better clinical improvement in knee health recovery and outcomes (as judged by KOOS Jr, OKS, NRS gait/walking ability and sleep, QoR-15, LoS).

Study Design

A prospective, double blinded RCT, with a single site cohort.

Patients and Methods

Patients who will be undergoing primary TKA for osteoarthritis will be eligible for this prospective study and randomised into two groups with 23 participants in each, one group receiving IORA Diclofenac (intervention group), and one group receiving IV Diclofenac (control group).

Power Calculation

There is a paucity of data evaluating the efficacy of IORA in pain management following TKA because it is a novel technique, although postoperative pain management is a thoroughly investigated area. Sample size was calculated based on previously published data investigating the efficacy of perioperative Celecoxib (a NSAID) on postoperative pain (VAS pain) after TKA [32]. This study showed statistically significant improvements in VAS pain scores for the intervention group (Celecoxib and PCA Morphine) at 48 hours and 72 hours after TKA, compared to the control group (PCA Morphine only). Mean VAS pain scores (in mm) in the intervention group were 21.3 ± 16.8 at 48 hours, and 17.8 ± 16.6 at 72 hours. Whereas VAS pain scores in the control group were 34.3 ± 15.0 at 48 hours, and 31.7 ± 20.1 at 72 hours.

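### The primary VAS-P analysis fixes no single contrast or unit of analysis, and two of the readings it allows do not hold the 5% level

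*Protocol*

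**What the plan says.** Under Postoperative Outcome Measurements, VAS-P is recorded at "1 hour, 2 hours, 3 hours, 4 hours, 5 hours, 12 hours, and 24 hours post-op", which is 7 readings. The diary follows: "Patients will also record twice daily VAS-P scores at 8am and 5pm from post-op day 1, up to post-op day 7", which is 2 × 7 = 14 more. The same section reduces the two diary scores of each day to a daily average.

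Data Capture and Analysis first asks for means, SDs and 95% confidence intervals at every recorded interval and calls this the primary objective. It then gives the method: "A general linear model or generalised linear mixed model, followed by independent two-sample t-test or Wilcoxon non-parametric rank sum test". Next comes: "VAS-P scores will be pooled according to the appropriate study group for comparison between the study arms". It adds that the choice of test will follow the distribution of the data.

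Objectives describes the primary outcome differently, as means over one week.

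The Power Calculation counts patients: "22 patients in each arm would provide >95% statistical power to detect the expected difference in pain relief (MCID of 20 mm"). The test level given there is 5%.

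**The concern.** Each patient contributes many correlated pain scores, and the text leaves open what enters the primary test. It could be each time point in turn, all scores of an arm together, or one summary per patient. These options have different error rates. Offering a mixed model does not settle the matter, because as the sentence is built the t-test or rank-sum step follows whichever model is chosen.

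This is the outcome on which superiority will be claimed, in a trial of 46 patients. If the analyst may choose among these routes after seeing the data, or takes one of the two that do not control the error, a false superiority claim becomes much more likely than the stated 5%.

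**Working it through.** **Inputs from the protocol.** 5% level (sidedness not stated; two-sided assumed); 22 per arm before dropout; difference 20 mm; source-study SDs 16.8 and 15.0 mm at 48 h, 16.6 and 20.1 mm at 72 h; 7 early and 14 diary readings. **Assumed:** within-patient correlation ρ, which the protocol does not give, taken as 0.1 to 0.7.

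**1. The protocol's own figure.** With one value per patient, power = Φ(20/(SD·√(2/22)) − 1.96).
- 48 h: SD = √((16.8² + 15.0²)/2) = 15.93. Then 20/(15.93 × 0.3015) = 4.16 and power = Φ(2.20) = 98.6%.
- 72 h: SD = √((16.6² + 20.1²)/2) = 18.43. Then 20/(18.43 × 0.3015) = 3.60 and power = Φ(1.64) = 94.9%.

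The stated power above 95% with 22 per arm is reproduced on the 48 h SD and nearly so on the 72 h SD. The calculation therefore works with one value per patient.

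**2. Values per patient.** Raw: 7 + 14 = 21. After daily averaging: 7 + 7 = 14.

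**3. Reading A: a separate test at each time point.** Each single test is valid, but there are many of them. Simulation with no true effect (10,000 trials per setting, 22 per arm, equal correlation between readings) gives this chance of at least one p<0.05:

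| ρ | 14 values | 21 readings |
|---|---|---|
| 0.3 | 44% | 56% |
| 0.5 | 36% | 43% |
| 0.7 | 26% | 30% |

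This is a multiplicity problem.

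**4. Reading B: all scores of an arm pooled and tested as independent.** Design effect DE = 1 + (m − 1)ρ; actual type I error = 2(1 − Φ(1.96/√DE)). For example, m = 21 and ρ = 0.5 give DE = 11, 1.96/√11 = 0.59, error 55%.

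| ρ | DE, m = 14 | error | DE, m = 21 | error |
|---|---|---|---|---|
| 0.1 | 2.3 | 20% | 3.0 | 26% |
| 0.3 | 4.9 | 38% | 7.0 | 46% |
| 0.5 | 7.5 | 47% | 11.0 | 55% |
| 0.7 | 10.1 | 54% | 15.0 | 61% |

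Simulation at ρ = 0.3, 0.5 and 0.7 agrees: 38%, 48%, 55% (14 values) and 46%, 55%, 62% (21 readings). With correlation that decays over successive readings (first-order, 0.8) it gives 44% and 47%. This is a clustering problem, distinct from Reading A.

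**5. Reading C: one mean per patient.** In all the simulated settings the type I error was 4.6% to 5.3%.

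**6. Weighting in a one-week mean.** If all values counted equally, the first five hours (5/168 = 3% of the week) would carry 5/21 = 24% of the weight, or 5/14 = 36% after daily averaging. The protocol does not prescribe equal weights; it prescribes none.

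**The case against.** A reader might infer that the plan treats up to 21 correlated readings per patient as independent. The document does not support that. Pooling by study group can simply mean collecting patients by arm. Diary scores are reduced to daily averages, and Objectives mentions a one-week mean, which could be formed per patient. A t-test at one time point, or on one mean per patient, respects independence. A general linear model is not wrong in itself either: repeated-measures forms exist, and ANCOVA on a patient mean is one. All of this stands, and the percentages under Reading B are therefore conditional.

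It is also fair that ρ is assumed and that model terms and covariance structure are commonly left to an analysis plan, which is not at hand. The protocol also says that a consultant statistician reviewed its statistical principles and will oversee the analysis.

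This does not remove the point. The protocol goes beyond leaving details open. It names a follow-on test, attaches the primary objective to every time point, and gives a different target in Objectives. The one reading that both holds 5% and yields a single conclusion is not the one written in the analysis section.

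**Conclusion.** The concern holds as a fault in what the protocol fixes: alternative models, a follow-on test, an unclear pooling sentence, and two different targets for the primary outcome, with no single contrast or unit of analysis. Reading A gives a 26% to 56% chance of some p<0.05 for ρ of 0.3 to 0.7. Reading B would give 20% to 54% (14 values) or 26% to 61% (21 readings) for ρ of 0.1 to 0.7. These ranges rest on the assumed ρ, mainly equal correlation, and a two-sided 5% level. They describe what the text permits, and should not be reported as the trial's actual error rate. It would be wrong to conclude that the protocol prescribes an analysis ignoring within-patient correlation. One mean per patient holds about 5% and agrees with the sample-size calculation.

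**What to change.** In Data Capture and Analysis, remove the t-test or rank-sum step as a primary test of VAS-P and name one primary analysis of the one-week VAS-P mean, in line with Objectives. Either of these would do:

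- a linear mixed model with a patient-level random effect or covariance structure and baseline VAS-P, with the between-arm difference in the one-week mean as the single primary contrast; or
- one one-week mean per patient, compared by ANCOVA on baseline VAS-P.

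Baseline VAS-P is already collected before surgery. State how the early readings and the daily averages are weighted in the mean, including how the 24-hour reading and the day-1 diary are handled together. Replace the pooling sentence with one that names the patient as the unit of analysis. Report individual time points descriptively, with confidence intervals.

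The cost is analysis wording, plus the ethics approval that the protocol requires for any modification. No new data are needed and the sample-size basis stays at patient level. The small downside is that p-values at single time points can no longer support the primary claim.

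### MME, KOOS Jr and OKS are fixed to unadjusted two-sample tests although their preoperative values are collected, which gives up precision in a 46-patient trial

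*Protocol*

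**What the plan says.** **Baseline data.** Under Preoperative Outcome Measurements the protocol says "The following outcome measurements will need to be completed by patients prior to their surgery" and lists, among others, VAS-P, opioid use converted to a baseline MME, KOOS Jr and OKS. The Patient Evaluation Schedule marks the same four preoperatively. Two uses are stated: averaging by study group, and, under Data Capture and Analysis, "Baseline characteristics and preoperative survey scores will be compared using a two sample t-test" or a rank sum test. The catastrophising score also serves as an exclusion criterion.

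**Secondary outcomes.** Data Capture and Analysis states: "For secondary objectives, independent two-sample t-test or Wilcoxon non-parametric rank sum test will be used to compare means of MME". The same sentence goes on to LoS, QoR-15, satisfaction, gait, sleep, OKS and KOOS Jr. Postoperative Outcome Measurements likewise says that clinic scores will be compared as group means at each time point.

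**Primary outcome.** VAS-P is analysed by a general linear model or generalised linear mixed model, followed by a t-test or rank sum test. No covariates are listed. The section adds "VAS-P scores will be pooled according to the appropriate study group for comparison between the study arms".

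**Size.** Patients are "randomised into two groups with 23 participants in each", and Power Calculation claims that "22 patients in each arm would provide >95% statistical power to detect the expected difference in pain relief (MCID of 20 mm" can be detected "at the 5% significance level between IORA Diclofenac and systemic (IV) Diclofenac".

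**The concern.** A two-sample t-test or rank sum test has no place for a covariate. For MME, KOOS Jr and OKS the protocol therefore collects the most obvious candidate predictor of each outcome and then names a method that ignores it. This is a stated choice of method, not a detail left for a later document. An analysis plan that used ANCOVA for these outcomes would depart from the protocol's own wording.

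The sentence on adjustments does not cure this. It closes the paragraph on normality, homogeneity and transformation, names no covariate, and makes any adjustment depend on the data.

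The planned baseline significance tests are no substitute. They do not change the outcome comparison, and at this size they miss imbalances that matter.

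At stake is the width of the confidence intervals for three secondary outcomes in a trial whose size was set for VAS-P alone. Preoperative opioid users are not excluded, so baseline MME will vary and may predict postoperative MME. The protocol gives no figure for how strongly.

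**Working it through.** **Inputs.** From the protocol: 23 randomised and 22 evaluable per arm; difference 20 mm; 5% significance (two-sided assumed); source-study SDs of 16.8 and 15.0 mm at 48 hours, and 16.6 and 20.1 mm at 72 hours. Assumed, because the protocol gives none: the within-arm baseline-outcome correlation r, taken over 0.1 to 0.5.

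**Step 1: the plan's own figure.** Pooled SD at 48 h = √((16.8² + 15.0²)/2) = 15.93 mm. At 72 h it is √((16.6² + 20.1²)/2) = 18.43 mm. Power for 20 mm with 22 per arm:
- SD 15.93: 0.986 (normal approximation), 0.9825 (noncentral t)
- SD 18.43: 0.949 (normal approximation), 0.940 (noncentral t)

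The stated figure is met with the 48 h SD and narrowly missed with the 72 h SD. I treat it as reproduced. The present point does not depend on it.

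**Step 2: what adjustment changes.** With n per arm and one estimated covariate, expected variance relative to the unadjusted comparison is

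ratio = (1 − r²) × (1 + 1/(2n − 4)).

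For n = 22 the second factor is 1 + 1/40 = 1.025, the price of estimating the slope. Residual degrees of freedom fall from 42 to 41. The equivalent unadjusted sample is 22/ratio per arm, and the change in standard error is √ratio − 1.

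| Assumed r | 1 − r² | Variance ratio | Change in SE | Equivalent n per arm |
|---|---|---|---|---|
| 0.1 | 0.99 | 1.015 | +0.7% | 21.7 |
| 0.2 | 0.96 | 0.984 | −0.8% | 22.4 |
| 0.3 | 0.91 | 0.933 | −3.4% | 23.6 |
| 0.4 | 0.84 | 0.861 | −7.2% | 25.6 |
| 0.5 | 0.75 | 0.769 | −12.3% | 28.6 |

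**Step 3: in terms of power.** The protocol gives no SD for MME, KOOS Jr or OKS, so effects are in SD units. The difference detectable with 80% power is 0.865 SD unadjusted, 0.836 SD at r = 0.3 and 0.759 SD at r = 0.5. For an illustrative effect of 0.6 SD, power is 49% unadjusted, 52% at r = 0.3 and 60% at r = 0.5. A simulation of 6,000 trials per setting agreed: 49% against 52% at r = 0.3, and 50% against 61% at r = 0.5.

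**Step 4: what a baseline test can see.** With 23 per arm the standard error of a baseline difference is √(2/23) = 0.295 SD. The chance of an imbalance above 0.3 SD in either direction on one measure is about 31%. A two-sided 5% test is significant only beyond about 0.59 SD. An imbalance of 0.5 SD would therefore pass as non-significant and, at r = 0.5, move the observed outcome difference by 0.5 × 0.5 = 0.25 SD.

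**The case against.** **Validity.** Under 1:1 randomisation the unadjusted tests are valid, and their type I error already allows for chance imbalance. A reader might infer from Step 4 that the results will be biased. The protocol does not support that: imbalance averages out over randomisations, and only efficiency is lost. This part of the objection stands.

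**The primary outcome.** A reader might also infer that VAS-P is analysed without baseline adjustment and that the trial is underpowered as a result. The protocol does not support this either. It begins with a general linear or mixed model, which can carry preoperative VAS-P, and its covariate list may be set in an analysis plan that is not shown. The sentence on pooling scores by group does not say that the comparison is unadjusted. Adjustment is neither secured nor ruled out, since a follow-on t-test or rank sum test is also named. Nor does the sample size turn on it: at the design difference of 20 mm with SD 18.43, power is 94.0% unadjusted, 95.3% at r = 0.3 and 98.0% at r = 0.5.

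**Unknown correlation.** The gain may be small. The preoperative visit may fall up to 6 months before surgery. Baseline MME is an average daily amount, while the outcome is total additional opioid use over a week under a standardised regimen. At r = 0.1 adjustment loses slightly. This stands, and is why a range is shown.

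**Distribution.** MME may be skewed, and many baseline values may be zero (an assumption). Plain ANCOVA would not deal with that, so the remedy has to allow a transformed or rank-based form.

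**Baseline tests.** The protocol does not make the outcome analysis depend on them. That is correct. The point is only that they should not come to decide adjustment through the open-ended adjustment sentence.

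**Conclusion.** The point holds for MME, KOOS Jr and OKS. The protocol collects a preoperative value for each and fixes tests that cannot use it. The cost is precision: nothing worth having at r of 0.2 or less, about 7% of variance at 0.3, 14% at 0.4 and 23% at 0.5. The price of adjusting is one degree of freedom and, at r = 0.1, a variance increase of about 1.5%. These figures assume 22 evaluable patients per arm, a linear relation between baseline and outcome, and correlations that the protocol does not supply.

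The point does not extend to LoS, QoR-15, satisfaction, gait or sleep, which have no baseline of their own in the protocol. For VAS-P it is a request for clarity, not a finding of error. It is a modest efficiency improvement and does not call the validity of the planned tests into question.

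**What to change.** In Data Capture and Analysis:

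1. For MME, KOOS Jr and OKS, replace the two-sample tests with ANCOVA at each planned time point (for MME, the one-week total), with the preoperative value of the same measure as covariate. State in advance the transformed or rank-based form to be used if the distribution requires it.
2. State that the general linear or mixed model for VAS-P includes preoperative VAS-P, and that the treatment effect and its confidence interval come from that model, not from a follow-on unadjusted test.
3. State that covariates are fixed in advance and that baseline significance tests play no part in choosing them. Descriptive baseline summaries by arm are enough.
4. Leave the two-sample comparisons for LoS, QoR-15, satisfaction, gait and sleep as they are.

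The cost is analysis wording, plus the Ethics Committee approval that the protocol requires for any modification. No new data, visits or patients are needed, because the covariates are already collected.
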